6.0 DOSE-LIMITING TOXICITIES AND DOSE MODIFICATIONS

6.1 Definitions of Dose-limiting Toxicity

DLTs are defined as clinically significant AEs or laboratory abnormalities occurring during the first cycle of study drug administration that are *at least possibly related* to either PLX2853 or carboplatin and clearly unrelated to disease progression, concurrent illness, or concomitant medication, and that meet one of the following CTCAE v5.0 criteria below. DLTs will be evaluated for the monotherapy safety lead-in subjects as well as each Phase 1b (PLX2853 + carboplatin) escalation cohort. Toxicities occurring in treatment Cycle 2 or later will be reviewed and their impact on subsequent dosing levels and frequency assessed.

In Phase 1b (PLX2853 + carboplatin), there will be a 24-hour delay between the first and subsequent subjects enrolled in each dose escalation cohort to maximize the safety of enrolled subjects.

Subjects participating in the optional Food Effect sub-study as well as the monotherapy safety lead-in will be DLT evaluable from the date of first dose and the DLT window for these patients will be 28 days from C1D1.

Subjects who are withdrawn from the study prior to completing the DLT assessment window for any reason other than a DLT will be replaced. Subject numbers must not be re-used.

DLTs are defined as follows:

• Hematologic Toxicities

- Grade 4 neutropenia lasting >7 days
- Grade ≥3 febrile neutropenia
- Grade 4 thrombocytopenia
- Grade ≥3 thrombocytopenia lasting >7 days or associated with clinically significant bleeding
- Grade 4 anemia

Non-hematologic Toxicities

- Any dose reduction required during Cycle 1 due to an AE
- Any treatment delay of >7 consecutive days during Cycle 1 due to study drug-related Grade ≥2 AEs that fail to resolve to baseline or Grade ≤1
- Any case of Hy's law defined as AST or ALT >3 × ULN with concurrent total bilirubin >2 × ULN, absence of cholestasis (elevated alkaline phosphatase (ALP) >2 × ULN), and no alternative etiology which can explain the combination of increased AST or ALT and total bilirubin, such as viral hepatitis A through E, other preexisting or acute liver disease, or another drug capable of causing the observed injury

- Any Grade ≥3 increase in AST/ALT (only for subjects without hepatic metastasis and with baseline values within normal limits)
- AST/ALT >5 × ULN for ≥14 days or any AST/ALT >8 × ULN (only for subjects with hepatic metastasis or with abnormal baseline values)

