- Grade 3 nausea, vomiting, or diarrhea that does not resolve to Grade ≤ 2 in ≤ 72 hours
- Any Grade 4 vomiting or diarrhea (life-threatening; urgent medical intervention indicated) irrespective of duration
- Any non-clinically significant Grade 3 or higher electrolyte imbalance that does not correct to Grade ≤1 in ≤5 days
- Any Grade 3 or Grade 4 clinically significant electrolyte imbalance (life-threatening; urgent medical intervention indicated) irrespective of duration
- Unless specifically noted in other DLT criteria any Grade ≥3 (AE or laboratory abnormality) toxicity that does not resolve to Grade ≤2 within 7 days despite maximal medical intervention, except for the following:
 - Grade 3 neuropathy in subjects with pre-existing Grade 2 neuropathy
- Any other Grade ≥3 toxicity (except those noted above) for which either the Principal Investigator or Sponsor deems further dose escalation inappropriate
- Carboplatin Cycle 2 Day 1 dose reduction (AUC not total dose) or carboplatin Cycle 2 Day 1 dose interruption for >7 days
 - An allergic reaction to carboplatin or any AEs associated with the allergic reaction during Cycle 1 will not be considered a DLT. The subject will be noted as inevaluable and will be replaced.
- Any death not clearly due to underlying disease or an extraneous cause

A subject who experiences a DLT may remain in the study and continue receiving study drug(s) at a lower dose if the Investigator deems the potential benefit outweighs the risk and that the subject is not eligible for, and/or interested in, an alternative therapy after consultation and agreement with the Medical Monitor.

AEs occurring in treatment Cycle 2 or later will be collected, analyzed, and discussed with the Study Committee to help inform the selection of doses for subsequent study cohorts, including the option of dose reduction. If cumulative toxicities are observed requiring dose reductions in 1 of 3 or more subjects, dose escalation may be halted and more subjects may be treated at that or a lower dose level.

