6.2 Dose Modification Guidelines

Reduction of dosing may take place for study drug-related AEs in Cycle 2 and beyond for subjects enrolled in the Phase 1b PLX2853 + carboplatin dose escalation cohorts or the safety

lead-in for the Phase 2a PLX2853 monotherapy part and at any time for subjects enrolled in the Phase 2a PLX2853 + carboplatin dose expansion cohorts and for subjects that are not part of the safety lead-in of the Phase 2a PLX2853 monotherapy part. Table 7 presents guidelines for dosage modification and re-treatment for PLX2853-related toxicities. These parameters are only a guide and are not intended to supersede the clinical judgment of the treating physician. Dose modifications of carboplatin should follow the label, as well as the guidance below.

If an allergic reaction to carboplatin occurs after Cycle 1, both PLX2853 and carboplatin should be held until a carboplatin desensitization protocol is conducted per institutional standard of care. Dosing of study drugs may resume after the subject's successful completion of a desensitization protocol and with approval from the Medical Monitor.

For the combination parts of the study, if 1 study drug needs to be held due to an AE, then both drugs need to be held until the AE resolves per the dose modification guidelines unless Medical Monitor approval is granted. If 1 study drug needs to be permanently discontinued, then both study drugs must be permanently discontinued and the subject taken off study unless approval granted by the Medical Monitor.

The dose modification/reduction guidelines are for clinically significant toxicities that are at least possibly related to PLX2853 administration. Definitions of "clinically significant" and "related" will be made based on the judgment of the Investigator, and the case should be discussed with the Medical Monitor as needed. All adjustments should be made in consultation with the Medical Monitor.

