			If not recovered to ANC ≥1.5 × 10 ⁹ /L after 7 days, discontinue permanently.
	2 nd Appearance	Discontinue permanently; provide growth factor support	N/A
Grade 3 or 4 thrombocytopenia without bleeding	1st Appearance of G3	Interrupt until PLT ≥75 × 10 ⁹ /L	If recovered to PLT ≥75 × 10 ⁹ /L ≤7 days, resume at same dose.
			If not recovered to PLT \geq 75 × 10 ⁹ /L after 7 days, reduce dose by 1 dose level.
	2 nd Appearance of G3 or 1 st Appearance of G4	Interrupt until PLT ≥75 × 10 ⁹ /L	If recovered to PLT ≥75 × 10 ⁹ /L in ≤7 days, reduce dose by 1 dose level.
			If not recovered to PLT ≥75 × 10 ⁹ /L after 7 days, reduce dose by 2 dose levels.
	3 rd Appearance of G3 or 2 nd Appearance of G4	Discontinue permanently	N/A

PLX2853-Related Toxicities	Frequency	When to Hold or Stop	Dose Adjustments for Resumption ^a
Grade 3 or 4 thrombocytopenia with clinically significant bleeding	1 st Appearance	Discontinue permanently	N/A
Other Grade 3 toxicities (excluding transaminase increases)	1st Appearance	Interrupt until resolved (Grade 0–1); start symptomatic treatment if possible	If recovered ≤5 days, resume at same dose.
			If symptoms persist for >5 days despite supportive management, reduce by 1 dose level.
	2 nd Appearance	Interrupt until resolved (Grade 0–1); start symptomatic treatment if possible	If recovered ≤5 days, reduce dose by 1 dose level.
			If symptoms persist for >5 days despite supportive management, discontinue permanently.
	3 rd Appearance	Discontinue permanently; start symptomatic treatment if possible	N/A
Grade 3 non- hematologic toxicities	1 st Appearance	Interrupt until resolved to Grade ≤1 or baseline	If recovered to Grade ≤1 or baseline in ≤14 days, restart at a reduced dose by 1 dose level.
			If symptoms persist at Grade ≥2 for >14 days, discontinue permanently.
Grade 4 non- hematologic toxicities	1st Appearance	Discontinue permanently; start symptomatic treatment if possible	N/A

PLX2853-Related Toxicities	Frequency	When to Hold or Stop	Dose Adjustments for Resumption ^a
Transaminase increases	• ALT or AST >8 × ULN but <20 × ULN	Immediately hold dose and discuss with Medical Monitor.	If clinically indicated, restart at a reduced dose.

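### In the monotherapy safety lead-in, a rapidly resolving Grade 3–4 toxicity that ends treatment in Cycle 1 is a DLT only by discretion, and Sections 6.1 and 7.1.5 disagree on whether that subject is replaced

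*Combined protocol and SAP*

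**What the plan says.** Section 6.1 applies one DLT list to the monotherapy safety lead-in and to the Phase 1b cohorts. Four of its criteria matter here:

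- Dose reduction: "Any dose reduction required during Cycle 1 due to an AE".
- Delay: more than 7 consecutive days off treatment in Cycle 1, "due to study drug-related Grade ≥2 AEs that fail to resolve to baseline or Grade ≤1".
- General clause, for toxicities not covered elsewhere in the list: "any Grade ≥3 (AE or laboratory abnormality) toxicity that does not resolve to Grade ≤2 within 7 days despite maximal medical intervention".
- Discretionary clause: any other Grade 3 or higher toxicity "for which either the Principal Investigator or Sponsor deems further dose escalation inappropriate".

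For Grade 4 non-hematologic toxicity at first appearance, Table 7 in Section 6.2 advises: "Discontinue permanently; start symptomatic treatment if possible". Section 6.2 describes the table as a guide that does not override the treating physician.

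On replacement, 6.1 states: "Subjects who are withdrawn from the study prior to completing the DLT assessment window for any reason other than a DLT will be replaced". Section 7.1.5 lists AEs among the reasons for being withdrawn from the study, but limits Cycle 1 replacement to reasons other than toxicity or clinically significant progression. Section 5.3.1 takes the same line for drug toxicity in Phase 1b. The synopsis text on the monotherapy part makes a subject non-evaluable for DLTs only when more than 25% of doses are missed for reasons other than an AE.

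Under Section 3.1.1 the lead-in has 6 subjects at 80 mg/day, and a DLT rate of 33% or more makes a committee convene to consider a dose reduction.

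**The concern.** The list ranks outcomes oddly. A toxicity managed by lowering the dose in Cycle 1 is automatically a DLT. A toxicity bad enough to end treatment is not, provided that it is unlisted and clears quickly. The replacement sentence in 6.1 then turns on whether the event was called a DLT, while 7.1.5 turns on whether it was toxicity. A subject who stops because of a non-DLT toxicity falls between the two.

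At stake is a consistent count in a group of six, where one subject decides whether the trigger is met. Two people applying the protocol to the same data could report different counts and make different replacement decisions.

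**Working it through.** **1. The plan's threshold.** Sections 3.1.2 and 5.3.1 equate 2 or more of 6 with 33% or more. This checks: 2/6 = 33.3% meets the limit and 1/6 = 16.7% does not. The lead-in trigger is therefore 2 DLTs.

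**2. The event against each criterion.** Take a lead-in subject with a related, unlisted Grade 4 non-hematologic toxicity that returns to Grade 1 or lower within 7 days and for which PLX2853 is stopped for good. A Grade 4 bilirubin rise outside Hy's law would be one example.

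| 6.1 criterion | Met? |
|---|---|
| Events named regardless of duration (e.g. Grade 4 vomiting or diarrhea, clinically significant electrolyte imbalance); AST/ALT and Hy's law rules | No: the event is not among them |
| General 7-day clause | No: resolved in time |
| Dose reduction | Not on its wording: treatment was stopped, and Table 7 treats reducing and stopping as different actions |
| Delay over 7 days | No: the AE resolved |
| Carboplatin at Cycle 2 Day 1 | Not applicable to monotherapy |
| Discretionary clause | Only if invoked; it is worded for dose escalation, and the lead-in plans none |

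A Grade 3 event with the same course fails the same criteria. For a first Grade 3 event that clears this fast, Table 7 advises resuming or reducing, so a stop there would rest on clinical judgment.

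**3. Replacement, if the subject also leaves the study.**

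- Section 6.1: must be replaced, unless the event was called a DLT.
- Section 7.1.5: not among those who may be replaced, because the reason is toxicity.
- Synopsis: the missed doses do not make the subject non-evaluable, because they were missed because of an AE.
- Section 3.1.1: omits the synopsis evaluability sentence, but allows extra subjects only where doses were missed for reasons other than an AE. This agrees with 7.1.5.

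**4. Effect on the count, with one other undisputed DLT.**

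- Event counted: 2/6 = 33.3%, trigger met.
- Subject kept as a non-DLT: 1/6 = 16.7%, not met.
- Subject replaced by one without a DLT: 7 treated, 1/6 = 16.7%, not met.

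**5. Likely size.** The documents give no rate for such events. The nearest figure is in Section 1.7: 68 subjects were treated in the two earlier studies, and the DLTs listed for them include one Grade 4 non-hematologic event, so u = 1/68 = 0.0147. That was hyperbilirubinemia at 140 mg/day. It was counted as a DLT there, and its time to resolution is not given. No Grade 4 non-hematologic DLT is listed at 80 mg/day total or below. The cohort sizes in Sections 1.8.1 and 1.8.2 give (3+3+4+3+4+6) + (3+4+3+3) = 23 + 13 = 36 subjects at those doses.

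Let T be an assumed total rate of treatment-limiting toxicity. The chance of reaching the trigger is P = 1 − (1−p)^6 − 6p(1−p)^5. Use p = T if all events count, p = T − u if the subject is kept as a non-DLT, and p = (T−u)/(1−u) if the subject is replaced.

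| T | All counted | Kept as non-DLT | Replaced |
|---|---|---|---|
| 0.30 | 1 − 0.118 − 0.303 = 0.580 | p = 0.285: 0.548 | p = 0.290: 0.557 |
| 0.20 | 1 − 0.262 − 0.393 = 0.345 | p = 0.185: 0.309 | p = 0.188: 0.315 |

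The loss is about 2 to 4 percentage points. It would be larger if such events were commoner. At T = 0.30 with u = 0.05, 0.10 or 0.15, the chance falls from 0.580 to 0.466, 0.345 or 0.224 if kept, and to 0.497, 0.399 or 0.287 if replaced. Nothing in the documents supports rates that high.

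**The case against.** The best case for leaving the text alone has four parts.

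- **Discretion is enough.** Either the Principal Investigator or the Sponsor can call the event a DLT, and Section 7.1.2 puts the Sponsor Medical Monitor and the participating Principal Investigators on the Study Committee. It is hard to picture a Grade 4 toxicity ending treatment with neither raising it. This makes a missed count unlikely, but leaves it a matter of judgment, whereas a lesser action (dose reduction) is automatic.
- **The replacement sentence concerns leaving the study.** Stopping the drug is not the same thing, and subjects off drug are still followed. This stands, and it limits the conflict to subjects who are also withdrawn from the study. Section 7.1.5 lists AEs as a reason for that, and 6.2 says interruptions over 2 weeks should generally lead to discontinuation from the study, so the case can arise.
- **Little follows from the trigger.** Under 3.1.1 the trigger only makes a committee convene to consider a reduction. The Study Committee convenes after the lead-in whatever the count, and dose decisions take in safety information from all enrolled subjects. This stands in full.
- **The size is borrowed.** The 1/68 figure comes from a higher dose and may not fit the case. This also stands.

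A reader might infer that Phase 1b has the same gap. For the most part it does not. In the combination parts, "If 1 study drug needs to be permanently discontinued, then both study drugs must be permanently discontinued and the subject taken off study", unless the Medical Monitor approves otherwise. Carboplatin is then not given at Cycle 2 Day 1, which can be read as meeting the criterion for "carboplatin Cycle 2 Day 1 dose interruption for >7 days".

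A reader might also infer that serious toxicity could go unseen or that an unsafe dose could go forward unreviewed. The documents do not support this, because the review in 3.1.1 and 7.1.2 does not depend on the DLT count.

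**Conclusion.** The point holds within narrow limits and is worth fixing. On the wording, a required Cycle 1 reduction for an AE is an automatic DLT, while permanent discontinuation for a related, unlisted Grade 4 (or Grade 3) non-hematologic toxicity that resolves to Grade 1 or lower within 7 days is a DLT only by discretion. If that subject is also withdrawn from the study, 6.1 and 7.1.5 give opposite instructions, and the synopsis sides with 7.1.5. With one other DLT, the same data read 1/6 or 2/6.

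The text does not support saying that 6.1 always drops such subjects: that needs both that the discretionary clause is not used and that the subject leaves the study as well as the drug.

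What is lost is a consistent count, not the safety review. The estimate of 2 to 4 percentage points rests on assumed total rates of 20% and 30% and on a rough proxy of 1.5% for the uncounted events. The conflict in the text rests on neither.

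**What to change.** 1. Reword the replacement sentence in 6.1 so that subjects are replaced only if they leave the DLT window for reasons other than drug toxicity. This matches 5.3.1 and 7.1.5.
2. Add a criterion to the DLT list in 6.1 and in the synopsis: permanent discontinuation of PLX2853 required during Cycle 1 because of a Grade 3 or higher AE at least possibly related to study drug, whatever its duration. Keep both existing exceptions: allergic reactions to carboplatin, and Grade 3 neuropathy in subjects who entered with Grade 2 neuropathy.

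Requiring that the stop be necessary, related and for Grade 3 or higher keeps an elective stop for a minor AE from becoming a DLT. The decision to stop remains clinical; only its counting is fixed.

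The cost is one sentence and one criterion in an amendment. The lead-in review would be triggered, or a Phase 1b dose level declared intolerable, slightly more often.

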6.2 Dose Modification Guidelines

Reduction of dosing may take place for study drug-related AEs in Cycle 2 and beyond for subjects enrolled in the Phase 1b PLX2853 + carboplatin dose escalation cohorts or the safety

lead-in for the Phase 2a PLX2853 monotherapy part and at any time for subjects enrolled in the Phase 2a PLX2853 + carboplatin dose expansion cohorts and for subjects that are not part of the safety lead-in of the Phase 2a PLX2853 monotherapy part. Table 7 presents guidelines for dosage modification and re-treatment for PLX2853-related toxicities. These parameters are only a guide and are not intended to supersede the clinical judgment of the treating physician. Dose modifications of carboplatin should follow the label, as well as the guidance below.

If an allergic reaction to carboplatin occurs after Cycle 1, both PLX2853 and carboplatin should be held until a carboplatin desensitization protocol is conducted per institutional standard of care. Dosing of study drugs may resume after the subject's successful completion of a desensitization protocol and with approval from the Medical Monitor.

For the combination parts of the study, if 1 study drug needs to be held due to an AE, then both drugs need to be held until the AE resolves per the dose modification guidelines unless Medical Monitor approval is granted. If 1 study drug needs to be permanently discontinued, then both study drugs must be permanently discontinued and the subject taken off study unless approval granted by the Medical Monitor.

The dose modification/reduction guidelines are for clinically significant toxicities that are at least possibly related to PLX2853 administration. Definitions of "clinically significant" and "related" will be made based on the judgment of the Investigator, and the case should be discussed with the Medical Monitor as needed. All adjustments should be made in consultation with the Medical Monitor.

If there is a PLX2853 dosing hold within a cycle (e.g., due to toxicity), study drug dosing will resume on the next appropriate day. For example, if the subject has a study drug hold for 10 days beginning on Cycle 2 Day 8 (Day 1 of hold), the subject should resume the schedule of events for Cycle 2 Day 18. If study assessments are missed during a hold, those assessments will be noted as not done and the next scheduled assessment day procedures will be followed. If the drug hold is less than 3 weeks between cycles, the first day of dosing in subsequent cycles should be considered Day 1, and all procedures calculated based on that starting day. For example, if the subject has a study drug hold on Cycle 2 Day 15 for 15 days, the subject will resume the schedule of events for Cycle 3 Day 1. Every attempt should be made to keep to the 28-day cycle.

In Cycle 2 and beyond, dose interruptions for Grade ≤2 non-hematologic toxicity can be implemented for up to 1 week at the discretion of the treating physician to manage clinically significant toxicities. No dose reduction is required when resuming treatment.

Dosing interruptions longer than 2 weeks should generally result in discontinuation from the study, unless the subject has demonstrated a clinical benefit from therapy and would like to continue dosing with study drug after discussion with the Sponsor and approval by the Medical Monitor.

Table 7: Recommended PLX2853 Dose Modifications

PLX2853-Related Toxicities	Frequency	When to Hold or Stop	Dose Adjustments for Resumption ^a
Grade 3 or 4 neutropenia	1 st Appearance	Interrupt until ANC recovers to ≥1.5 × 10 ⁹ /L; growth factor support permitted	If recovered to ANC \geq 1.5 × 10 ⁹ /L in \leq 7 days, resume at same dose. If not recovered to ANC \geq 1.5 × 10 ⁹ /L after 7 days, reduce dose by
	2 nd Appearance	Interrupt until ANC	1 dose level. If recovered to ANC ≥1.5 × 10 ⁹ /L in
	2 Appearance	recovers to $\ge 1.5 \times 10^9/L$; growth factor support permitted	≤7 days, reduce dose by 1 dose level.
			If not recovered to ANC \geq 1.5 × 10 ⁹ /L after 7 days, reduce dose by 2 dose levels.
	3 rd Appearance	Discontinue permanently; growth factor support permitted	N/A
Grade 3 or 4 febrile neutropenia	1st Appearance	Interrupt until ANC and fever recover; provide growth factor support	If recovered to ANC $\geq 1.5 \times 10^9/L$ and T $\leq 38^{\circ}$ C in ≤ 7 days, reduce dose by 1 dose level.
			If not recovered to ANC ≥1.5 × 10 ⁹ /L after 7 days, discontinue permanently.
	2 nd Appearance	Discontinue permanently; provide growth factor support	N/A
Grade 3 or 4 thrombocytopenia without bleeding	1st Appearance of G3	Interrupt until PLT ≥75 × 10 ⁹ /L	If recovered to PLT ≥75 × 10 ⁹ /L ≤7 days, resume at same dose.
			If not recovered to PLT \geq 75 × 10 ⁹ /L after 7 days, reduce dose by 1 dose level.
	2 nd Appearance of G3 or 1 st Appearance of G4	Interrupt until PLT ≥75 × 10 ⁹ /L	If recovered to PLT ≥75 × 10 ⁹ /L in ≤7 days, reduce dose by 1 dose level.
			If not recovered to PLT ≥75 × 10 ⁹ /L after 7 days, reduce dose by 2 dose levels.
	3 rd Appearance of G3 or 2 nd Appearance of G4	Discontinue permanently	N/A

PLX2853-Related Toxicities	Frequency	When to Hold or Stop	Dose Adjustments for Resumption ^a
Grade 3 or 4 thrombocytopenia with clinically significant bleeding	1 st Appearance	Discontinue permanently	N/A
Other Grade 3 toxicities (excluding transaminase increases)	1st Appearance	Interrupt until resolved (Grade 0–1); start symptomatic treatment if possible	If recovered ≤5 days, resume at same dose.
			If symptoms persist for >5 days despite supportive management, reduce by 1 dose level.
	2 nd Appearance	Interrupt until resolved (Grade 0–1); start symptomatic treatment if possible	If recovered ≤5 days, reduce dose by 1 dose level.
			If symptoms persist for >5 days despite supportive management, discontinue permanently.
	3 rd Appearance	Discontinue permanently; start symptomatic treatment if possible	N/A
Grade 3 non- hematologic toxicities	1 st Appearance	Interrupt until resolved to Grade ≤1 or baseline	If recovered to Grade ≤1 or baseline in ≤14 days, restart at a reduced dose by 1 dose level.
			If symptoms persist at Grade ≥2 for >14 days, discontinue permanently.
Grade 4 non- hematologic toxicities	1st Appearance	Discontinue permanently; start symptomatic treatment if possible	N/A

PLX2853-Related Toxicities	Frequency	When to Hold or Stop	Dose Adjustments for Resumption ^a
Transaminase increases	• ALT or AST >8 × ULN but <20 × ULN	Immediately hold dose and discuss with Medical Monitor.	If clinically indicated, restart at a reduced dose.
	 ALT or AST 5 × ULN for more than 2 weeks ALT or AST 3 × ULN and total bilirubin >2 × ULN or INR >1.5 (in absence of anticoagulation) ALT or AST 3 × ULN with the appearance of fatigue, nausea, vomiting, right upper quadrant pain or tenderness, fever, rash, and/or eosinophilia (>5%) 	Institute close monitoring. Any decision to restart after transaminases return to baseline must be discussed with the Medical Monitor.	
	Hy's Law: AST/ALT 3 × ULN and total bilirubin >2 × ULN and ALP <2 × ULN with no alternative etiology for the observed injury ALT or AST >20 × ULN	Discontinue permanently	N/A
QTcF >500 msec or 60 msec increase from baseline verified on repeat ECG	1st Appearance	Interrupt study drug until resolved.	Upon recovery to QTc ≤500 msec (Grade ≤2), restart at a reduced dose. Permanently discontinue study drug if the QTc interval remains >500 msec and increased >60 msec from pretreatment values (after controlling cardiac risk factors for QT prolongation, e.g., electrolyte abnormalities, congestive heart failure, and bradyarrhythmias).b

 $ALP = alkaline \ phosphatase; \ ALT = alanine \ aminotransferase; \ ANC = absolute \ neutrophil \ count; \ AST = aspartate \ aminotransferase; \ ECG = electrocardiogram; \ G = grade; \ INR = International \ Normalized \ Ratio; \ N/A = not \ applicable; \ PLT = platelet; \ QTcF = AT \ interval \ corrected \ using \ Fridericia's \ equation; \ T = temperature; \ ULN = upper \ limit \ of \ normal$

^a See Table 6 for dose levels.

^b QTc: Only 1 dose reduction is permitted per subject. Prior to and following treatment initiation or after dose modification of study drugs for QTc prolongation, evaluate ECG and electrolytes (including potassium, magnesium, and calcium) after 15 days, and monthly thereafter or more often as clinically indicated.

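### Table 7 gives two incompatible dose instructions for a first Grade 3 non-hematologic event that recovers within 5 days

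*Combined protocol and SAP*

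**What the plan says.** Table 7 in Section 6.2 sets out recommended PLX2853 dose modifications by toxicity and by appearance. After the rows for neutropenia, febrile neutropenia and thrombocytopenia, two rows deal with Grade 3 events in general terms.

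- **The 'Other' row**, labelled "Other Grade 3 toxicities (excluding transaminase increases"). At first appearance dosing is held until Grade 0 or 1. Then: "If recovered ≤5 days, resume at same dose", and "If symptoms persist for >5 days despite supportive management, reduce by 1 dose level". The row also has second- and third-appearance entries. At the second, the longer-lasting case reads "If symptoms persist for >5 days despite supportive management, discontinue permanently"; the third leads to permanent discontinuation.
- **The non-hematologic row**, for Grade 3 non-hematologic events, with no exclusions. It has a first-appearance entry only: "If recovered to Grade ≤1 or baseline in ≤14 days, restart at a reduced dose by 1 dose level", and "If symptoms persist at Grade ≥2 for >14 days, discontinue permanently".

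The text before the table adds a general rule: "Dosing interruptions longer than 2 weeks should generally result in discontinuation from the study". It makes an exception for a subject who is benefiting clinically and wishes to go on with treatment, subject to discussion with the Sponsor and Medical Monitor approval. Section 6.2 also describes the table as guidance that yields to the treating physician's judgement, and it requires Medical Monitor consultation for adjustments. Footnote a refers the reader to Table 6 for the dose levels.

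**The concern.** A first Grade 3 event such as fatigue or hyponatremia fits both row labels. If it resolves quickly, one row keeps the dose and the other lowers it by a level, so two sites that each follow Table 7 could give different PLX2853 doses after the same event.

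Three further provisions depend on the answer:

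- Section 6.2 allows reductions at any time in the Phase 2a combination expansion and for monotherapy subjects outside the safety lead-in. For those subjects the ambiguity applies from Cycle 1. In Phase 1b and the safety lead-in, reductions are provided for from Cycle 2.
- Section 6.1 lets escalation be halted when cumulative toxicity requires dose reductions in 1 of 3 or more subjects. Whether a short-lived Grade 3 event in Cycle 2 or later counts can depend on the row read.
- Section 7.1.8 lists departures from the dose-reduction and interruption rules as a category of protocol deviation. Two opposed rows make that hard to judge consistently.

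**Working it through.** The plan states no figure to reproduce here, so the check sets the two rows side by side and then looks for a rule of precedence.

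**Step 1. Both rows applied to one first Grade 3 non-hematologic, non-transaminase event (not a QTcF event), by time to recovery.**

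| Time to recovery | 'Other' row | Non-hematologic row | Result |
|---|---|---|---|
| 5 days or less | same dose | down 1 level | incompatible |
| 6 to 14 days | down 1 level | down 1 level | agree |
| more than 14 days, still Grade 2 or higher | down 1 level (no upper time limit) | permanent stop | differ |

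The general 2-week rule largely covers the last line. What remains open is that rule's clinical-benefit exception, which the non-hematologic row does not carry. The rows also differ on when the hold ends: only the non-hematologic row accepts return to baseline.

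**Step 2. Search for a tie-breaker in Section 6.2 and the Table 7 footnotes.**

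- The guidance-only statement and the Medical Monitor consultation apply to the whole table and rank neither row.
- The paragraph on short interruptions for non-hematologic toxicity stops at Grade 2.
- The 2-week rule does not reach recovery in 5 days or less.
- Footnote a points only to the dose levels; footnote b concerns QTc.

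None of these settles which row applies.

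**Step 3. Size of the difference for recovery in 5 days or less** (Table 6, Section 3.1.2).

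| Starting level | Same dose | One level lower | Difference |
|---|---|---|---|
| 2 | 80 mg/day | 40 mg/day | (80 − 40)/80 = 50% |
| 1 | 40 mg/day | 20 mg/day | (40 − 20)/40 = 50% |
| −1 | 20 mg/day | 20 mg/day | 0% for PLX2853; the levels differ in carboplatin target AUC, (5 − 4)/5 = 20% |
| −2 | 20 mg/day | none listed | not defined |

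Table 6 lists combination levels. Using it for monotherapy (80 versus 40 mg/day) is an assumption that rests on footnote a.

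**Step 4. Does this type of event occur?** Section 1.7 reports 1 DLT in this study, 4 in PLX124-01 and 2 in PLX124-02: 1 + 4 + 2 = 7. Three of the 7 include a Grade 3 non-hematologic, non-transaminase event: hyponatremia in this study, and fatigue and hyperbilirubinemia in the two earlier ones. The other four are two Grade 4 thrombocytopenias, one Grade 3 thrombocytopenia and one Grade 4 hyperbilirubinemia. This shows that such events arise, not how often they recover within 5 days.

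**The case against.** The best defence is that 'Other' means not covered by any other row. The 'Other' row would then keep only residual events such as Grade 3 anemia, and the conflict would disappear. The table already needs some such convention: the non-hematologic row, read literally, also takes in Grade 3 transaminase and QTcF events, which have rows of their own. A first-appearance-only entry is not unusual either, since the QTcF row has one too.

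This reading is possible, but it is nowhere stated and it fits the table poorly. The 'Other' row expressly excludes transaminase increases. These are non-hematologic and have their own row, so under the residual reading the exclusion is redundant. The reading also leaves second and third Grade 3 non-hematologic events without a rule, because only the 'Other' row supplies one. The table therefore has either a conflict or a gap.

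The second defence is practical: the table is advisory and the Medical Monitor is consulted. That stands as a limit on the consequences, and single cases may well be settled sensibly. But the Medical Monitor works from the same two rows.

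The third defence concerns the hyponatremia example, and it also stands. That event was a Cycle 1 DLT. Section 6.1 has separate text on continuing after a DLT, Section 6.2 limits reductions in Cycle 1 of Phase 1b, and the recovery time is not given. It shows that the event type occurs, not that the row conflict arose. It is also fair to say that Table 7 concerns PLX2853, so reading a carboplatin change into the step from Dose Level −1 is an inference.

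**Conclusion.** The concern holds. For a first PLX2853-related Grade 3 non-hematologic, non-transaminase event that recovers in 5 days or less, Table 7 gives two instructions that exclude each other, and no text ranks them. The consequence is a twofold difference in PLX2853 dose from Dose Level 2 or 1, no PLX2853 difference from Dose Level −1, and an undefined step from Dose Level −2. The dose conflict does not extend to recovery in 6 to 14 days. Beyond 14 days only the clinical-benefit exception is left unreconciled.

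The conclusion rests on the row labels as written and, for monotherapy, on applying Table 6 there. The documents give no rate or recovery time for Grade 3 non-hematologic events, so the number of subjects affected cannot be estimated. No effect on ORR, sample size, alpha or power is claimed. It should be fixed because it bears on consistent dosing and subject safety.

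**What to change.** The sponsor's clinical team should reconcile the two Grade 3 rows with each other and with the 2-week interruption rule in Section 6.2, including its clinical-benefit exception. After the change, each event, at each appearance and for each recovery time, should lead to one action. The revision should state which events each row covers and where repeat non-hematologic events are handled. This review takes no view on which instruction is right.

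The cost is table wording in a protocol amendment, with no added procedures or subjects.
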